7.6. ECOG Performance Status

A by-subject listing will be provided for ECOG Performance Status assessments by subject ID number and visit in chronological order.

7.7. Other Safety Measures

No additional safety measures are specified in the protocol.

7.8. Changes from Protocol-Specified Safety Analyses

There are no deviations from the protocol-specified safety analyses.

8. PHARMACOKINETIC ANALYSES

8.1. PK Sample Collection

PK samples will be collected at the time points listed in Protocol 6.2.11.

8.2. PK Analyses Related to Intensive PK Sampling

Concentrations of GS-5829 and its metabolite in plasma will be determined using validated bioanalytical assays. The first dose and steady-state PK will be determined in subjects in the PK analysis set.

8.2.1. Estimation of Pharmacokinetic Parameters

Pharmacokinetic (PK) parameters will be estimated using Phoenix WinNonlin® software using standard noncompartmental methods. The linear/log trapezoidal rule will be used in conjunction with the appropriate noncompartmental model, with input values for dose level, dosing time, plasma concentration, and corresponding real-time values, based on drug dosing times whenever possible.

All predose sample times before time-zero will be converted to 0.

For area under the curve (AUC), samples BLQ of the bioanalytical assays occurring prior to the achievement of the first quantifiable concentration will be assigned a concentration value of 0 to prevent overestimation of the initial AUC. Samples that are BLQ at all other time points will be treated as missing data in WinNonlin. The nominal time point for a key event or dosing interval (τ) may be used to permit direct calculation of AUC over specific time intervals. The appropriateness of this approach will be assessed by the PK scientist on a profile-by-profile basis.

Pharmacokinetic parameters such as AUC_{tau} , λ_z and $t_{1/2}$ are dependent on an accurate estimation of the terminal elimination phase of drug. The appropriateness of calculating these parameters will be evaluated upon inspection of PK data on a profile-by-profile basis by the PK scientist.

8.2.2. Pharmacokinetic Parameters

Pharmacokinetic parameters will be generated for all subjects in the PK analysis set for whom PK parameters can be derived. The analytes presented in [Table 8-1](#) will be evaluated if data are available.

Table 8-1. Pharmacokinetic Parameters for Each Analyte

	GS-5829	GS-697412
Cycle 1 Day 1 (enzalutamide combination groups)	C_{\max} , T_{\max} , AUC_{0-24h} , AUC_{last} , C_{24h} , C_{last} , T_{last} , λ_Z , $T_{1/2}$	C_{\max} , T_{\max} , AUC_{0-24h} , AUC_{last} , C_{24h} , C_{last} , T_{last} , λ_Z , $T_{1/2}$,
Cycle 1 Day 8 (monotherapy group, fasted) Cycle 2 Day 1 (monotherapy group, fed)	C_{\max} , T_{\max} , AUC_{tau} , AUC_{last} , C_{tau} , C_{last} , T_{last} , λ_Z , $T_{1/2}$, V_Z F, CL_{SS} F	C_{\max} , T_{\max} , AUC_{tau} AUC_{last} , C_{tau} , C_{last} , T_{last} , λ_Z , $T_{1/2}$,
Cycle 1 Day 15 (enzalutamide combination group)	C_{\max} , T_{\max} , AUC_{tau} , AUC_{last} , C_{tau} , C_{last} , T_{last} , λ_Z , $T_{1/2}$, V_Z F, CL_{SS} F	C_{\max} , T_{\max} , AUC_{tau} AUC_{last} , C_{tau} , C_{last} , T_{last} , λ_Z , $T_{1/2}$,

Individual subject concentration data and individual subject PK parameters will be listed and summarized using descriptive statistics by treatment. Summary statistics (n, mean, StD, coefficient of variation [%CV], median, min, max, Q1, and Q3) will be presented for both individual subject concentration data by time point and individual subject PK parameters by treatment. Moreover, the geometric mean, 95% CI, and the mean and StD of the natural log-transformed values will be presented for individual subject PK parameter data.

Individual concentration data listings and summaries will include all subjects with concentration data. The sample size for each time point will be based on the number of subjects with nonmissing concentration data at that time point. The number of subjects with concentration BLQ will be presented for each time point.

Individual PK parameter data listings and summaries will include all subjects for whom PK parameter(s) can be derived. The sample size for each PK parameter will be based on the number of subjects with nonmissing data for that PK parameter.

The following tables will be provided for each analyte by treatment:

- Individual subject concentration data and summary statistics
- Individual subject plasma PK parameters and summary statistics

The following figures may be provided for each analyte by treatment:

- Mean (\pm StD) concentration data versus time (on linear and semilogarithmic scales)
- Median (Q1, Q3) concentration data versus time (on linear and semilogarithmic scales)

Individual, mean, and median postdose concentration values that are \leq LLOQ will not be displayed in the figures and remaining points connected.

PK sampling details by subject, including procedures, differences in scheduled and actual draw times, and sample age will be provided in listings.

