Enzalutamide is a strong CYP3A4 inducer, which has been demonstrated to decrease the AUC of a CYP3A4 substrate (midazolam) by 86%; therefore further dose escalation of the combination therapy will be performed in these subjects prior to initiation Phase 2 Dose Expansion. As the concern is for decreased GS-5829 exposure, the initial dose level of the combination therapy will be 160 mg of enzalutamide combined with a starting dose of GS-5829 that has been determined to be safe and tolerable in the single agent dose escalation. Enzalutamide dosing will begin approximately 2 weeks prior to GS-5829 dosing to achieve near maximal CYP3A4 induction to reduce changes in GS-5829 exposure over the first cycle. PK evaluations will be performed and if indicated and supported by PK, safety and tolerability, additional cohorts with higher doses and/or more frequent dosing (ie, twice daily) of GS-5829 in combination with enzalutamide may be tested. The total daily dose will not increase by more than 100% in the next cohort.

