### **5.3. Dosage and Administration of GS-5829 and Enzalutamide**

GS-5829 tablets will be provided by Gilead Sciences, Inc. and will be taken orally. Initiation of treatment with the study drug will take place after enrollment and cohort assignment. Subjects will take their dose of study drug at approximately 24-hour intervals. To reduce inter-subject variability on efficacy and safety, subjects will be instructed to take GS-5829 approximately 1 hour before or 2 hours after a meal, unless otherwise specified by protocol. Grapefruit juice is prohibited while on study drug. In one or more monotherapy dose levels or in the monotherapy expansion (Group 1), on Day 1 of Cycle 2, approximately 10 subjects may be asked to administer GS-5829 in fed state with a standardized meal (~500 to 600 calories and ~30% of calories from fat). If evaluation of food effect cannot be performed on Cycle 2, Day 1, it may be performed at a visit after Cycle 2, Day 1 (where subject has taken at least 7 consecutive days of GS-5829), if necessary.

XTANDI® (enzalutamide) will be supplied as 40 mg capsules for oral administration. Subjects assigned to receive enzalutamide in combination with GS-5829 in this study will orally self-administer 4 capsules of enzalutamide (160 mg total daily dose) once daily at approximately 24-hour intervals beginning on Study Day 1 and GS-5829 will start, at the assigned dose, 14 days ( $\pm$  3 day window) later on Cycle 1 Day 1. Subjects enrolled into Group 3 should be on at least 12 weeks of continuous enzalutamide treatment prior to starting Cycle 1 Day 1. Capsules should be swallowed whole and may be taken with or without food. Refer to [Appendix 9](#) for further details.

If the subject misses a dose, he should be instructed to take the study drug as soon as he remembers, unless more than 8 hours have elapsed since the scheduled time of the missed dose. In this case, the subject should be instructed to wait and take the next dose at the regularly scheduled time. Subjects should not take more than 1 dose of study drug at a time.

If a subject vomits within 5 minutes of dosing and the tablet is visible, the subject should be instructed to re-dose. If a subject vomits more than 5 minutes after dosing or if the tablet is not visible, the subject should be instructed to wait and take the next dose at the regularly scheduled time.

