#### **Phase 1b Dose Escalation:**

##### **Monotherapy Dose Escalation**

PK and PD samples for GS-5829 will be collected on Day 8 of Cycle 1 at pre-dose, 0.5, 1, 2, 3, 4, 6, 8, and 24 hours post-dose, as well as pre-dose and 1-4 hours after GS-5829 administration on Day 1 and Day 15 of Cycle 1 and anytime on Day 1 of Cycles 2 through 6.

At one or more dose levels, PK samples may be collected on Day 1 of Cycle 2 at pre-dose and 0.5, 1, 2, 3, 4, 6, 8, and 24 hours post-dose after GS-5829 has been administered in the fed state. If evaluation of food effect cannot be performed on Cycle 2, Day 1, it may be performed at a visit after Cycle 2, Day 1, if necessary.

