1.2. Study Design

This study has two phases: Phase 1b dose escalation and Phase 2 dose expansion.

Phase 1b: This is an open-label, multicenter, sequential dose-escalation study to evaluate the safety, tolerability, PK, and pharmacodynamics (PD) of GS-5829 as a single agent, and combined with enzalutamide in subjects with metastatic castrate-resistant prostate cancer (mCRPC).

Dose Escalation of GS-5829

Subjects with mCRPC who have progressed on either abiraterone and/or enzalutamide will be sequentially enrolled at progressively higher dose levels to receive oral GS-5829 as a single agent once daily. Dose escalation [3+3] will be performed with cohort sizes of 3 to 6 subjects. Initially 3-4 subjects will be enrolled into each dose level. The study will be initiated at a dose level that has been demonstrated to be safe and tolerable in the ongoing Phase 1 study in patients with solid tumors and lymphomas (Study GS-US-350-1599).

The dose levels for single agent GS-5829 once daily are 2, 3, 4, 6 and 9mg. Dose levels may be modified based on emerging safety, PK, PD, and efficacy results.

Dose Escalation of GS-5829 and enzalutamide

The combination dose escalation using 3+3 design may initiate prior to identification of the MTD of single agent GS-5829 using a starting dose of GS-5829 that has been determined to be safe and tolerable in the single agent dose escalation. The first 3-4 subjects to enroll will receive GS-5829 at a dose less than or equal to the previously determined single agent MTD (or a monotherapy dose that has been determined to be safe) combined with enzalutamide.

Enzalutamide is a strong CYP3A4 inducer, which is expected to decrease the exposure of GS-5829 and therefore a higher dose of GS-5829 may be required to achieve target coverage compared to the single agent dose. Subjects will administer enzalutamide 160 mg once daily as a single agent starting on Study Day 1 through Cycle 1, Day 1. On Cycle 1 Day 1 (approximately 14 days after Study Day 1), subjects will administer GS-5829 once daily in combination with enzalutamide 160 mg once daily in order to evaluate the interaction of the 2 agents. Depending on the observed PK interaction, toxicity and tolerability observed in the single agent dose escalation, the dose escalation may continue beyond a dose which has been identified to be safe and tolerable in the single agent arm. Any increase in the dose of GS-5829 will not be by more than 100% in the next cohort.

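### SAP 8.2.2 plans no fed/fasted exposure ratio, so the food effect is not estimated with an interval and the within-subject pairing goes unused; the enzalutamide ratio, between-subject by design, is also not planned

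*SAP*

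**What the plan says.** **Food effect.** Protocol 5.3 says that on Day 1 of Cycle 2, in one or more monotherapy dose levels or in Group 1, "approximately 10 subjects may be asked to administer GS-5829 in fed state with a standardized meal". Protocol 6.2.11 gives the fed sampling times and allows a later visit: "If evaluation of food effect cannot be performed on Cycle 2, Day 1", it may be done afterwards. Table 8-1 in SAP 8.2.2 derives the same parameters for both occasions, in one row labelled "Cycle 1 Day 8 (monotherapy group, fasted) Cycle 2 Day 1 (monotherapy group, fed").

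**Enzalutamide.** SAP 1.2, repeating Protocol 3.2, has GS-5829 added to enzalutamide on Cycle 1 Day 1 "in order to evaluate the interaction of the 2 agents". Protocol 1.3.1 explains the lead-in: "Enzalutamide dosing will begin approximately 2 weeks prior to GS-5829 dosing to achieve near maximal CYP3A4 induction". The steady-state combination profile is the Table 8-1 row "Cycle 1 Day 15 (enzalutamide combination group").

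**Analysis.** SAP 8.2.2 states: "Individual subject concentration data and individual subject PK parameters will be listed and summarized using descriptive statistics by treatment". For the PK parameters, "the geometric mean, 95% CI, and the mean and StD of the natural log-transformed values will be presented", alongside the usual n, mean, StD, CV, median, quartiles and range. SAP section 8 names no ratio, paired difference or model. SAP 8.2.3 (PK/PD) is marked not applicable. SAP 3.7 mentions model fitting in a rule for values below quantitation, and SAP section 9 lists two bioequivalence guidances, but no method is attached to either. Protocol 8.7 is also purely descriptive.

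**The concern.** A food-effect evaluation asks how much exposure changes when the same person takes the drug with food. The answer is a ratio and an interval for that ratio. Two geometric means with two separate intervals do not give the second part.

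The separate summaries may not even cover the same people. SAP 8.2.2 includes every subject for whom a parameter can be derived, so the fasted summary can contain subjects who never had a fed profile. A ratio of the two tabulated means would then mix the food effect with a difference between subjects.

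There is also a labelling gap. Table 8-1 lists the fed profile only at Cycle 2 Day 1 and SAP 3.8.2 summarises by nominal visit, while Protocol 5.3 and 6.2.11 allow the fed day to fall later.

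For enzalutamide, PK alone and in combination is a phase 1b secondary objective, and no combination/monotherapy ratio is planned. What is at stake is how well the study report can describe these two effects.

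**Working it through.** **No figure to reproduce.** The documents give no CV, target precision or confidence level for either comparison. The only related number is the approximately 10 fed subjects in Protocol 5.3. All CVs below are assumptions, shown as ranges.

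**Notation.** Log-scale variance is s² = ln(1 + CV²):

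- within-subject CV 20%: 0.0392; 30%: 0.0862
- between-subject CV 40%: 0.1484; 60%: 0.3075

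**Fed/fasted, n = 10, 90% CI.** The interval is the estimated ratio multiplied and divided by a factor.

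Paired: factor = exp( t(0.95, n−1) × √(2·s_w²/n) ), with t(0.95, 9) = 1.833.

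- CV 20%: exp(1.833 × √(2 × 0.0392/10)) = exp(1.833 × 0.0886) = 1.18
- CV 30%: exp(1.833 × 0.1313) = 1.27

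Pairing ignored: factor = exp( t(0.95, 2n−2) × √(2·(s_w² + s_b²)/n) ), with t(0.95, 18) = 1.734.

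- within 20%, between 40%: exp(1.734 × √(2 × 0.1876/10)) = exp(1.734 × 0.1937) = 1.40
- within 20%, between 60%: exp(1.734 × 0.2633) = 1.58
- within 30%, between 40%: exp(1.734 × 0.2166) = 1.46
- within 30%, between 60%: exp(1.734 × 0.2806) = 1.63

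Around a ratio of 1, with CVs of 20% within and 40% between, the interval is 0.85 to 1.18 paired and 0.71 to 1.40 with pairing ignored.

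**Fewer subjects.** SAP section 1 says phase 2 was not started, so fed profiles can come only from phase 1b monotherapy cohorts. At n = 6 (t = 2.015 on 5 df; 1.812 on 10 df) the same formulas give 1.26 to 1.41 paired and 1.57 to 1.93 with pairing ignored.

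**Combination/monotherapy, between subjects, 90% CI.** Factor = exp( t(0.95, n₁+n₂−2) × s × √(1/n₁ + 1/n₂) ), at one matched dose, total CV 30% to 70% (s = 0.294 to 0.632).

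- 3 versus 3 (t = 2.132): 1.67 to 3.00
- 6 versus 6 (t = 1.812): 1.36 to 1.94

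At 6 versus 6 and CV 50% (factor 1.64), an estimated ratio of 0.50 has an interval of about 0.30 to 0.82. The ratio is informative only for a large effect, and no analysis choice makes it paired.

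**The case against.** The strongest reply is that the protocol never promised these contrasts. Its PK objective and endpoint name parameters, Protocol 8.7 is descriptive, and SAP 3.5 plans no formal testing. That is fair as history: a reader might infer that the SAP dropped a planned analysis, and it did not. But a ratio with an interval is estimation, not testing, and the SAP already gives intervals for PK parameters.

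Second, the pairing is not destroyed. Individual parameters are listed, so anyone can form each subject's ratio. This stands: the pairing is unused, not lost.

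Third, a reader might infer that pairing is forgone for enzalutamide too. The documents rule that out. Combination subjects start enzalutamide about two weeks before GS-5829 and have no GS-5829-alone profile. For that contrast, the log-scale mean, StD and n per group are enough to build a matched-dose interval by hand, so the omission costs less there.

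Fourth, the fed profile is optional in Protocol 5.3 and 6.2.11 (the synopsis is firmer for phase 1b), so 10 subjects are not assured. This stands.

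Fifth, the unpaired interval in the working is not an analysis the SAP plans. It shows what the group summaries alone would support.

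**Conclusion.** The point holds as a low-cost improvement. SAP 8.2.2 leaves the food effect without a ratio or interval and does not use a pairing that the design provides. With 10 subjects, using it brings the 90% CI factor to 1.18-1.27, against 1.40-1.63 when it is ignored. These figures rest on assumed CVs of 20-30% within and 40-60% between subjects, and on 10 subjects with both profiles. The enzalutamide ratio is also missing, but there the most that can be added is an imprecise between-group estimate.

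A reader might infer that combination dose choice hangs on this omission. The documents do not support that. Protocol 3.2 bases the choice on PK, tolerability, safety and PSA response together, with a safety review team assessing each cohort. SAP section 1 records that the study stopped during escalation with all subjects off drug. The primary endpoint is untouched. Exploratory objectives are blacked out, so a food-effect objective may exist there, but it would not supply a method in SAP section 8.

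**What to change.** **(a) Main.** Add to SAP 8.2.2 a fed/fasted geometric mean ratio with 90% CI for AUCtau and Cmax, from a paired or mixed-model analysis of log values with subject as the pairing unit. Include subjects with both profiles at the same dose, and take the fed profile at whichever visit it was collected. Relabel the Table 8-1 row to match. If no fed profiles were collected, say so in one line.

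**(b) Exploratory.** Add a combination Cycle 1 Day 15 / monotherapy Cycle 1 Day 8 geometric mean ratio with CI, as a between-group comparison at matched or normalised dose. Protocol 1.3.1 allows twice-daily GS-5829 in combination cohorts, so use exposure over a common 24-hour interval or restrict to once-daily cohorts. State the dose-proportionality assumption. State also that the groups differ in eligibility: combination subjects may not have had prior enzalutamide, while monotherapy subjects may have progressed on it (Protocol 4.2).

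The cost is two short analyses on data already planned for collection. Fixing the subjects, parameters and confidence level before the database is finalised also avoids a ratio chosen after the data are seen.

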8.2.3. PK/PD Analyses

Not applicable.

10. SOFTWARE

SAS® Software Version 9.4. SAS Institute Inc., Cary, NC, USA.

nQuery Advisor(R) Version 8.3. Statistical Solutions, Cork, Ireland.

11. SAP REVISION

Revision Date (DD MMM YYYY)	Section	Summary of Revision	Reason for Revision

12. APPENDICES

Appendix 1. Schedule of Assessments

Study Procedures Table – Phase 1b and 2 Monotherapy

Study Phase	Screening		First 28 Days			Cycle 2 Day 1 and Every 4 weeks	Every 12 weeks	EOT	30-day Safety Follow-up ¹⁸	Survival Follow-Up ²⁰
Cycle Day	Day -28	Cycle 1 Day 1*	Day 8	Day 15	Day 22					
Window (day)	-28		±1	±2	±3	±7	±7	±7	±7	
Informed Consent	X									
Medical and Medication History ¹	X									
Physical Examination ²	X	X	X	X	X	X		X	X	
ECOG Performance Status	X	X	X		X	X		X	X	
Vital Signs ³	X	X	X	X	X	X		X	X	
Triplectate 12 lead ECG ⁴	X	X	X			X		X		
Adverse events/Concomitant medications ⁷	X	X	X	X	X	X	X	X	X	
GS 5829 Accountability and/or Dispensing ⁵		X				X		X		
Dosing Diary Accountability and/or Dispensing		X				X		X		
Enrollment	X									
CBC with Differential	X ⁸	X	X	X	X	X		X	X	

Study Phase	Screening		First 28 Days			Cycle 2 Day 1 and Every 4 weeks	Every 12 weeks	EOT	30-day Safety Follow-up ¹⁸	Survival Follow-Up ²⁰
Cycle Day	Day -28	Cycle 1 Day 1*	Day 8	Day 15	Day 22					
Window (day)	-28		±1	±2	±3	±7	±7	±7	±7	
Chemistry	X ⁸	X	X	X	X	X		X	X	
Coagulation ⁹	X ⁸	X	X					X		
Urinalysis	X ⁸	X	X			X		X	X	
GS 5829 Intensive PK ¹⁰		X	X			X				
GS 5829 Sparse PK ¹⁰		X		X		X				
GS 5829 pharmacodynamic ¹¹		X	X	X		X				
CCI										
Tumor Markers PSA ¹³		X				X		X		
Archival Tumor Tissue ¹⁴		X								
CCI										
CT/MRI ¹⁶	X						X	X		
Radionuclide Bone Scan ¹⁷	X						X	X		

Study Phase	Screening		First 28 Days			Cycle 2 Day 1 and Every 4 weeks	Every 12 weeks	EOT	30-day Safety Follow-up ¹⁸	Survival Follow-Up ²⁰
Cycle Day	Day -28	Cycle 1 Day 1*	Day 8	Day 15	Day 22					
Window (day)	-28		±1	±2	±3	±7	±7	±7	±7	
Treatment Response Assessment ¹⁹							X	X		
Phone call										X

* Day 1 pre GS 5829 lab samples may be drawn up to two days prior to the Day 1 visit.

- 1 Medical history includes significant past medical events (eg, prior hospitalizations or surgeries), a review of the disease under study, prior anti cancer therapies, historical PSA levels and any concurrent medical illnesses.
- 2 Screening and End of Treatment Physical Examinations (PE) will be a complete PE. Beginning at C1D1, a modified physical examination will be performed. Weight (without shoes) should be measured at each PE. Height (without shoes) is measured at Screening only.
- 3 C1D1 Vital Signs will be taken within 15 min pre GS 5829 dose and 2 and 4 hours post dose (+/- 15 min); vital signs will be taken pre dose only at all subsequent visits. Oxygen saturation will be tested with a pulse oximeter.
- 4 Triplicate ECG will be collected at any time during Screening window, Day 1 of Cycles 2 6 (at pre dose), and at EOT. In Phase 1b monotherapy, triplicate ECGs will be collected on C1D1 at pre dose and 1 4 hrs post dose and on C1D8 at pre dose, 1 hour, 2 hours, 3 hours, 4 hours, 6 hours, and 8 hours post dose (+/- 20 min). In Phase 2 dose expansion, triplicate ECGs will be collected on C1D1 at pre dose and 1 4 hrs post dose and on C1D8 at pre dose, 1 hour, 2 hours, 4 hours, and 6 hours post dose (+/- 20 min). ECGs should always be collected prior to PK (or any other blood draw) if they are to be collected at the same nominal time point. Subjects should be resting quietly and free of distraction (eg, TV, conversation) for 10 minutes prior to ECG collection and ECGs should be collected over a 5 minute window at each time point.
- 5 Administer GS 5829 in a fed state on C2D1 in selected dose level.
- 6 Beginning on C1D1, subjects will receive GS 5829 daily.
- 7 Adverse event reporting period begins once the Informed Consent Form has been signed. AEs will be assessed using NCI CTCAE (v 4.03) criteria at pre and post GS 5829 dosing during applicable clinic visits. Subjects will also return to clinic at 30 day post last IP dose to assess AEs and SAEs. At screening, all medications taken up to 30 days prior to screening will be documented in the eCRF.
- 8 Screening chemistry, hematology, coagulation, and urinalysis to be collected within 7 days of C1D1 for central lab assessment.
- 9 Coagulation assessment includes PT/PTT, fibrinogen, Factor VII, fibrinogen degradation products (FDP).
- 10 In Phase 1b monotherapy: plasma samples for GS 5829 PK will be collected on Day 8 of Cycle 1 at pre dose, 0.5, 1, 2, 3, 4, 6, 8, and 24 hours post dose as well as pre dose and 1 4 hours after GS 5829 administration on Day 1 and Day 15 of Cycle 1 and anytime on Day 1 of Cycles 2 through 6. At one or more dose levels, PK samples will be collected on Day 1 of Cycle 2 at pre dose and 0.5, 1, 2, 3, 4, 6, 8, and 24 hours post dose. (C2D1: If intensive PK is collected for that cohort, then sparse PK does not need to be collected.) In Phase 2 dose expansion Group 1: PK samples will be collected on Day 8 of Cycle 1 at pre dose and 1, 2, 4, and 6 hours post dose. Sparse PK samples will be collected at pre dose and 1 4 hours post dose on Cycle 1 Day 1 and Day 15 and anytime on Day 1 of Cycles 2 through 6.

11 In Phase 1b monotherapy: PD biomarker sampling will be collected at pre dose, 0.5, 1, 2, 3, 4, 6, 8 and 24 hours post dose relative to GS 5829 administration on Cycle 1 Day 8. PD samples will also be collected pre dose and 1-4 hours post dose on Cycle 1 Day 1 and Cycle 1 Day 15. Additional PD samples will be collected at anytime on Day 1 of Cycles 2 through 6. In phase 2 dose expansion Group 1: PD samples will be collected on Day 8 of Cycle 1 at pre dose and 1, 2, 4, and 6 hrs post dose. Sparse PD will be collected at pre dose and 1-4 hours post dose on Cycle 1 Day 1 and Day 15 and anytime on Day 1 of Cycles 2 through 6.

CCI

13 Tumor markers PSA will be collected on C1D1 at pre dose and on Day 1 of every subsequent Cycle at pre dose.

14 If available, paraffin embedded archival tumor tissue block for shipment to Gilead or its designee will be requested at C1D1.

CCI

16 Tumor evaluation by CT/MRI or applicable scan will be performed during screening (within 8 weeks of Cycle 1 Day 1) and every 12 weeks thereafter. The same radiographic procedure used to define measurable lesions must be used throughout the study for each subject. CT/MRI to be done at EOT visit if not done within the previous 4 weeks.

17 Subjects will also undergo a bone scan. Scan at EOT visit is not necessary if the previous scan is performed within 4 weeks of the EOT.

18 For Phase 1b Dose Escalation subjects, the 30 Day Safety Follow Up will be the final study visit. Phase 2 Dose Expansion subjects will complete the 30 Day Safety Follow Up Visit and proceed to Long Term Survival Follow Up.

19 Tumor burden as assessed by PCWG2 Guidelines.

20 LTFU will begin for subjects participating in phase 2 after the 30 day Safety Follow Up visit for up to 2 years after the last dose of IP.

Study Procedures Table – Phase 1b and 2 Combination Therapy

Study Phase	Screening	Study Day 1		First 28 Days			Cycle 2 Day 1 and Every 4 weeks	Every 12 weeks	EOT	30-day Safety Follow-up ¹⁸	Survival Follow-Up ²⁰
Cycle Day	Day -28			Cycle 1 Day 1*	Day 8	Day 15	Day 22				
Window (day)	-28	3		±3	±1	±2	±3	±7	±7	±7	±7
Informed Consent	X										
Medical and Medication History ¹	X										
Physical Examination ²	X	X	X	X	X	X	X		X	X	
ECOG Performance Status	X	X	X	X		X	X		X	X	
Vital Signs ³	X	X	X	X	X	X	X		X	X	
Triple 12 lead ECG ⁴	X		X		X		X		X		
Adverse events/Concomitant medications ⁷	X	X	X	X	X	X	X	X	X	X	
GS 5829/enzalutamide Accountability and/or Dispensing ⁵			X				X		X		
Enzalutamide Accountability and/or Dispensing ⁶		X	X				X		X		
Dosing Diary Accountability and/or Dispensing			X				X		X		

Study Phase	Screening	Study Day 1		First 28 Days			Cycle 2 Day 1 and Every 4 weeks	Every 12 weeks	EOT	30-day Safety Follow-up ¹⁸	Survival Follow-Up ²⁰
Cycle Day	Day -28		Cycle 1 Day 1*	Day 8	Day 15	Day 22					
Window (day)	-28	3	±3	±1	±2	±3	±7	±7	±7	±7	
Enrollment	X										
CBC with Differential	X ⁸	X	X	X	X	X	X		X	X	
Chemistry	X ⁸	X	X	X	X	X	X		X	X	
Coagulation ⁹	X ⁸	X	X	X					X		
Urinalysis	X ⁸	X	X	X			X		X	X	
GS 5829 Intensive PK ¹⁰			X		X		X				
GS 5829 Sparse PK ¹⁰			X		X		X				
GS 5829 pharmacodynamic ¹¹			X	X	X		X				
CCI											
Tumor Markers PSA ¹³			X				X		X		
Archival Tumor Tissue ¹⁴			X								
CCI											
CT/MRI ¹⁶	X								X	X	

Study Phase	Screening	Study Day 1		First 28 Days			Cycle 2 Day 1 and Every 4 weeks	Every 12 weeks	EOT	30-day Safety Follow-up ¹⁸	Survival Follow-Up ²⁰
Cycle Day	Day -28		Cycle 1 Day 1*	Day 8	Day 15	Day 22					
Window (day)	-28	3	±3	±1	±2	±3	±7	±7	±7	±7	
Radionuclide Bone Scan ¹⁷	X							X	X		
Treatment Response Assessment ¹⁹								X	X		
Phone call											X

* Day 1 pre GS 5829 lab samples may be drawn up to two days prior to the Day 1 visit.

- 1 Medical history includes significant past medical events (eg, prior hospitalizations or surgeries), a review of the disease under study, prior anti cancer therapies, historical PSA levels and any concurrent medical illnesses.
- 2 Screening and End of Treatment Physical Examinations (PE) will be a complete PE. Beginning at C1D1, a modified physical examination will be performed. Weight (without shoes) should be measured at each PE. Height (without shoes) is measured at Screening only.
- 3 Study Day 1 vital signs will be take 15 min pre enzalutamide dose. C1D1 Vital Signs will be taken within 15 min pre GS 5829 dose and 2 and 4 hours post dose (+/- 15 min); vital signs will be taken pre dose only at all subsequent visits. Oxygen saturation will be tested with a pulse oximeter.
- 4 Triplicate ECG will be collected at any time during Screening window, Day 1 of Cycles 2-6 (at pre dose), and at EOT. In Phase 1b dose escalation with enzalutamide, triplicate ECGs will be collected on Cycle 1, Day 1 and Day 15 at pre dose, 1 hour, 2 hours, 3 hours, 4 hours, 6 hours, and 8 hours post dose (+/- 20 min). In Phase 2 dose expansion, triplicate ECGs will be collected on C1D1 and C1D15 at pre dose and 1-4 hrs post dose and on C2D1 at pre dose, 1 hour, 2 hours, 4 hours, and 6 hours post dose (+/- 20 min). ECGs should always be collected prior to PK (or any other blood draw) if they are to be collected at the same nominal time point. Subjects should be resting quietly and free of distraction (eg, TV, conversation) for 10 minutes prior to ECG collection and ECGs should be collected over a 5 minute window at each time point.
- 5 Administer GS 5829 in a fed state on C2D1 in selected dose level.
- 6 Subjects in phase 1b dose escalation with enzalutamide and Phase 2 Group 2 receive enzalutamide alone beginning on Study Day 1, then in combination with GS 5829 beginning C1D1.
- 7 Adverse event reporting period begins once the Informed Consent Form has been signed. AEs will be assessed using NCI CTCAE (v 4.03) criteria at pre and post GS 5829 dosing during applicable clinic visits. Subjects will also return to clinic at 30 day post last IP dose to assess AEs and SAEs. At screening, all medications taken up to 30 days prior to screening will be documented in the eCRF.
- 8 Screening chemistry, hematology, coagulation, and urinalysis to be collected within 7 days of C1D1 for central lab assessment.
- 9 Coagulation assessment includes PT/PTT, fibrinogen, Factor VII, fibrinogen degradation products (FDP).
- 10 In Phase 1b dose escalation with enzalutamide: PK samples will be collected on Day 1 and Day 15 of Cycle 1 at pre dose 0.5, 1, 2, 3, 4, 6, 8 and 24 hours post dose and anytime on Day 1 of Cycles 2 through 6. In Phase 2 dose expansion Group 2: PK samples will be collected on Cycle 2, Day 1 at pre dose and 1, 2, 4, and 6 hours post dose. Sparse PK will be collected at pre dose and 1-4 hours post dose on Cycle 1 Day 1 and Day 15 and anytime on Day 1 of Cycles 3 through 6.

11 In Phase 1b dose escalation with enzalutamide: PD biomarker samples will be collected on Day 1 and Day 15 of Cycle 1 at pre dose, 0.5, 1, 2, 3, 4, 6, 8, and 24 hours post dose and anytime on Day 1 of Cycles 2 through 6. In Phase 2 dose expansion Group 2: PD samples will be collected on Day 15 of Cycle 1 at pre dose and 1, 2, 4, and 6 hrs post dose. Spare PD will be collected at pre dose and 1 4 hours post dose on Cycle 1 Day 1 and Day 8 and anytime on Day 1 of Cycles 2 through 6.

CCI

13 Tumor markers PSA will be collected on C1D1 at pre dose and on Day 1 of every subsequent Cycle at pre dose.

14 If available, paraffin embedded archival tumor tissue block for shipment to Gilead or its designee will be requested at C1D1.

CCI

16 Tumor evaluation by CT/MRI or applicable scan will be performed during screening (within 8 weeks of Cycle 1 Day 1) and every 12 weeks thereafter. The same radiographic procedure used to define measurable lesions must be used throughout the study for each subject. CT/MRI to be done at EOT visit if not done within the previous 4 weeks.

17 Subjects will also undergo a bone scan. Scan at EOT visit is not necessary if the previous scan is performed within 4 weeks of the EOT.

18 For Phase 1b Dose Escalation subjects, the 30 Day Safety Follow Up will be the final study visit. Phase 2 Dose Expansion subjects will complete the 30 Day Safety Follow Up Visit and proceed to Long Term Survival Follow Up.

19 Tumor burden as assessed by PCWG2 Guidelines.

20 LTFU will begin for subjects participating in phase 2 after the 30 day Safety Follow Up visit for up to 2 years after the last dose of IP.
